### 3.2 Exclusion Criteria

Subjects meeting any of the criteria below may not participate in the study:

1. Prior therapy for stage III NSCLC
2. Mixed histology with small cell lung cancer will not be allowed.
3. Sequential chemoradiation will not be permitted.
4. Induction and consolidation chemotherapy (separate from concurrent chemoradiation) will not be allowed.
5. Prior exposure to anti-PD-1 or anti-PD-L1 antibodies including durvalumab.
6. Current or prior use of immunosuppressive medication within 14 days before the first dose of durvalumab. The following are exceptions to this criterion:
  - Intranasal, inhaled, topical steroids, or local steroid injections (e.g., intra articular injection)
  - Systemic corticosteroids at physiologic doses not to exceed <<10 mg/day>> of prednisone or its equivalent
  - Steroids as premedication for hypersensitivity reactions (e.g., CT scan premedication)
7. History of pulmonary fibrosis, interstitial lung disease, or pneumonitis requiring steroids.
8. Active or prior documented autoimmune disease within the last 2 years. Patients with vitiligo, stable hypothyroidism, Grave's disease, or psoriasis not requiring systemic treatment are not excluded.
9. Body weight < 30 kg
10. Active and ongoing steroid use, except for non-systemically absorbed treatments (such as inhaled or topical steroid therapy for asthma, COPD, allergic rhinitis).
11. Active infection requiring systemic therapy.
12. Uncontrolled current illness that in the opinion of the investigator renders the investigational treatment plan unsafe.
13. Receipt of live attenuated vaccine within 30 days prior to the first dose of IP. Note: Patients, if enrolled, should not receive live vaccine whilst receiving IP and up to 30 days after the last dose of IP.

14. Major surgical procedure (as defined by the Investigator) within 28 days prior to the first dose of IP. NOTE: Local surgery of isolated lesions for palliative intent is acceptable.
15. Active other malignancy; exceptions include basal cell or squamous cell skin cancer, in situ cervical or bladder cancer.
16. Active infection including tuberculosis (clinical evaluation that includes clinical history, physical examination and radiographic findings, and TB testing in line with local practice), hepatitis B (known positive HBV surface antigen (HBsAg) result), hepatitis C Patients with a past or resolved HBV infection (defined as the presence of hepatitis B core antibody [anti-HBc] and absence of HBsAg) are eligible. Patients positive for hepatitis C (HCV) antibody are eligible only if polymerase chain reaction is negative for HCV RNA.
17. Treatment with any investigational drug within 30 days prior to registration.
18. History of organ transplantation (including allogeneic stem cell transplantation).
19. Other medical or psychiatric conditions that in the opinion of the site investigator would preclude safe participation in this protocol.

### 3.3 Eligibility Criteria for Consolidation Durvalumab

1. Patients must have recovered from toxicities associated with prior chemoradiation to CTCAE < Grade 2.
2. Patients must not have progressed following chemoradiation therapy, as measured on imaging per RECIST 1.1.
3. Confirmation of ECOG Performance Status of 0 or 1.
4. Any grade pneumonitis from prior chemoradiation will not be permitted.

### 4. SUBJECT REGISTRATION

All subjects must be registered through HCRN's electronic data capture (EDC) system. A subject is considered registered when an "On Study" date is entered into the EDC system. Subjects must be registered prior to starting protocol therapy.

### 5. TREATMENT PLAN

This is a single arm study of induction durvalumab at 1500 mg intravenously (IV) on Day 1 of a four week cycle for 1 cycle, followed by concurrent definitive chemoradiation, followed by consolidation durvalumab at 1500 mg IV Day 1 of every 4 week cycle for up to 12 cycles.

Chemoradiation should begin no earlier than 4 weeks and no later than 5 weeks after the dose of induction durvalumab. Patients meeting required criteria for consolidation and without disease progression after chemoradiation should begin consolidation durvalumab within 1-42 days after

completion of chemoradiation. Subjects unable to start within the timeframes described should be discussed with the sponsor-investigator. Concurrent chemoradiation will be with platinumbased chemotherapy (cisplatin or carboplatin, with etoposide, taxane, or pemetrexed) selected at the treating physician's discretion. Patients receiving different chemotherapeutic agents will be analyzed together for toxicity, with exploratory analysis of toxicity related to different chemotherapeutic regimens. Radiation will be administered using standard fractionation at a dose of 54-66 Gy.

## 5.1 Induction Durvalumab Administration

Drug	Dose	Route	Schedule 	Cycle Length	Total # of Cycles
Durvalumab	1500 mg	Intravenously (IV) over 1 hour	Day 1	4 weeks	1

 A window of  $\pm$  3 days may be applied to all study visits to accommodate observed holidays, inclement weather, scheduling conflicts etc. Date and time of each drug administration should be clearly documented in subject's chart and electronic case report forms (eCRFs).

### 5.1.1 Durvalumab

Durvalumab will be administered over 1 hour ( $\pm$  15 minutes). Please refer to the current IB for more detailed information.

Patients will be monitored before, during and after the infusion with assessment of vital signs. Patients are monitored (pulse rate, blood pressure) every 30 minutes (with a window of - 5 minutes/+ 10 minutes), during the infusion period (including times where infusion rate is slowed or temporarily stopped). In the event of a  $\leq$  Grade 2 infusion-related reaction, the infusion rate of durvalumab may be decreased by 50% or interrupted until resolution of the event and re-initiated at 50% of the initial rate until completion of the infusion. For patients with a  $\leq$  Grade 2 infusion related reaction, subsequent infusions may be administered at 50% of the initial rate.

Acetaminophen and/or an antihistamine (eg, diphenhydramine) or equivalent medications per institutional standard may be administered at the discretion of the investigator. If the infusion related reaction is  $\geq$  Grade 3 or higher in severity, study drug will be discontinued.

As with any antibody, allergic reactions to dose administration are possible. Appropriate drugs and medical equipment to treat acute anaphylactic reactions must be immediately available, and study personnel must be trained to recognize and treat anaphylaxis. The study site must have immediate access to emergency resuscitation teams and equipment in addition to the ability to admit patients to an intensive care unit if necessary

For management of patients who experience an infusion reaction, please refer to the toxicity and management guidelines in Appendix A.

## 5.2 Chemotherapy and Radiation Therapy Administration

### 5.2.1 Chemotherapy Administration

Concurrent chemoradiation will be with platinum-based chemotherapy (cisplatin or carboplatin, with etoposide, taxane, or pemetrexed) selected at the treating physician's discretion. The chemotherapy regimen used should be administered per institutional standards following the prescribing guidelines for each drug. Information regarding chemotherapy regimen used will be captured in the EDC system.

### 5.2.2 Radiation Therapy Administration

Treatment will be delivered using IMRT or 3DCRT using typically 6-10MV photons per institutional standards. 4D simulation and appropriate IGRT are encouraged. Radiation therapy must begin within one week of the first day of chemotherapy (or vice versa). Therapy will be 1.8-2 Gy per day; 5 days per week, excluding holidays per institutional standard as this is a standard of care regimen for this patient population. 54-66 Gy will be delivered. Interruptions in radiation treatment are strongly discouraged. Dose interruptions are allowed, however, for toxicity management at treating investigator discretion to align with institutional standard of care.

### 5.3 Consolidation Durvalumab Administration

Drug	Dose	Route	Schedule 	Cycle Length	Total # of Cycles
Durvalumab	1500 mg	Intravenously (IV) over 1 hour	Day 1	4 weeks	12

 A window of  $\pm$  3 days may be applied to all study visits to accommodate observed holidays, inclement weather, scheduling conflicts etc. Date and time of each drug administration should be clearly documented in subject's chart and electronic case report forms (eCRFs).

### 5.4 Safety Run In-Portion

This study will include an initial safety run-in portion. The dose limiting toxicity (DLT) period is through completion of induction durvalumab, chemoradiation, and 2 cycles of consolidation durvalumab. Enrollment will pause after the first 5 patients are enrolled. If 3 out of the first 5 patients experience dose limiting toxicities during the DLT period, further enrollment will be halted, and subsequent accrual re-evaluated with site investigators and the sponsor-investigator. If stopping criteria are not met, enrollment will continue, and accrual will again pause after 10 total patients are enrolled.

If 4 out of the first 10 patients experience dose limiting toxicities (DLT) during the DLT period, further enrollment will be halted, and subsequent accrual re-evaluated with site investigators and the sponsor-investigator. If stopping criteria are not met, enrollment will then continue for the full planned cohort. Patients in the safety run-in phase will be analyzed for PFS and outcomes as members of the full study cohort.

Subjects in the safety run in group who do not remain on the study through completion of the DLT period for reasons other than DLT will be replaced with another subject.

#### 5.4.1 Definition of Dose Limiting Toxicities

The DLT period is through completion of induction durvalumab, chemoradiation, and 2 cycles of consolidation durvalumab. NCI Common Terminology Criteria for Adverse Events (CTCAE) v5 will be used in grading adverse events. A DLT will be defined as:

- Any grade of febrile neutropenia regardless of duration or reversibility  Any Grade 4 immune-mediated adverse event (imAE)  Any grade of immune-mediated neurotoxicity.
- Grade  $\geq$  3 colitis
- Grade 3 non-infectious pneumonitis irrespective of duration
- Grade 2 pneumonitis that does not resolve to  $\leq$  Grade 1 within 3 days of the initiation of maximal supportive care
- Grade 3 imAE, excluding colitis or pneumonitis, that does not downgrade to Grade 2 within 3 days after onset of the event despite optimal medical management including systemic corticosteroids or does not downgrade to  $\leq$  Grade 1 or baseline within 14 days
- Grade 3 liver transaminase elevation with concurrent total bilirubin  $> 2 \times$  ULN  Grade  $\geq$  3 non-imAE, except for the exclusions listed below

The following conditions are excluded from the DLT definition:

- Grade 3 fatigue lasting  $\leq$  7 days
- Grade 3 endocrine disorder (thyroid, pituitary, and/or adrenal insufficiency) that is managed with or without systemic corticosteroid therapy and/or hormone replacement therapy and the subject is asymptomatic
- Grade 3 inflammatory reaction attributed to a local antitumor response (eg, inflammatory reaction at sites of metastatic disease, lymph nodes, etc)
- Concurrent vitiligo or alopecia of any AE grade
- Grade 3 infusion-related reaction (first occurrence and in the absence of steroid prophylaxis) that resolves within 6 hours with appropriate clinical management
- Grade 3 or 4 neutropenia that is not associated with fever or systemic infection that improves by at least 1 grade within 3 days.
- Grade 3 or 4 lymphopenia
- Grade 3 thrombocytopenia that is not associated with clinically significant bleeding that requires medical intervention and improves by at least 1 grade within 3 days
- Isolated Grade 3 electrolyte abnormalities that are not associated with clinical signs or symptoms and are reversed with appropriate maximal medical intervention within 3 days
- Transient asymptomatic laboratory abnormalities that do not require hospitalization

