## 5.6 Supportive Care

Subjects should receive appropriate supportive care measures as deemed necessary by the site investigator. Suggested supportive care measures for the management of adverse events with potential immunologic etiology are outlined below. Where appropriate, these guidelines include the use of oral or intravenous treatment with corticosteroids as well as additional antiinflammatory agents if symptoms do not improve with administration of corticosteroids. Note that several courses of steroid tapering may be necessary as symptoms may worsen when the steroid dose is decreased. For each disorder, attempts should be made to rule out other causes such as metastatic disease or bacterial or viral infection, which might require additional supportive care. The treatment guidelines are intended to be applied when the investigator determines the events to be related to Durvalumab.

Early recognition of signs and symptoms potentially related to an inflammatory or immunemediated mechanism is important for proper management of toxicities. For guidance on identifying, evaluating, and treating imAE, see the Toxicity Management Guidelines in Appendix A.

ImAE observed with anti PD-L1/PD-1 agents may include pneumonitis, hepatitis, diarrhea/colitis and intestinal perforation, endocrinopathies (hypo- and hyper-thyroidism, adrenal insufficiency, hypophysitis/hypopituitarism and Type 1 diabetes mellitus), nephritis, rash/dermatitis, pancreatitis, myocarditis, myositis/polymyositis and rare/less frequent imAE including neuromuscular toxicities such as myasthenia gravis and Guillain-Barre syndrome.

Other inflammatory responses that are rare with a potential immune-mediated etiology are also considered as imAE and include, but are not limited to, pericarditis, sarcoidosis, uveitis and other events involving the eye, skin, hematological and rheumatological events. It is possible that events with an inflammatory or immune mediated mechanism could occur in nearly all organs.

In addition, infusion-related reactions and hypersensitivity/anaphylactic reactions with a different underlying pharmacological etiology are also considered imAEs (Durvalumab IB).

For guidelines on the treatment of immune-mediated adverse events, please refer to the published ASCO guidelines [14].

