### 13. TRIAL MANAGEMENT

#### 13.1 Data and Safety Monitoring Plan (DSMP) HCRN

oversight activities include:

- Review and processing of all adverse events requiring expedited reporting as defined in the protocol
- Provide trial accrual progress, safety information and data summary reports to the sponsor-investigator
- Submit data summary reports to the DSMB for review according to DSMB Charter

This study will have a Data and Safety Monitoring Board (DSMB). The DSMB is chaired by an independent medical oncologist external to this trial. The DSMB will provide a recommendation to the sponsor-investigator after all information is reviewed. This information will also be provided to HCRN who will distribute to the site investigator/participating sites for submission to their respective IRB according to the local IRB's policies and procedures.

The DSMB review will include but is not limited to:

- Adverse event summary report
- Audit results if applicable

- Data related to stopping/decision rules described in study design
- Study accrual patterns
- Protocol deviations

The DSMB will meet after the first 5 patients are enrolled and have completed 2 cycles of consolidation durvalumab, or after 3 patients of the first 5 in the safety run-in cohort have experienced DLT (whichever comes first), to review data for stopping rules as above. The DSMB will again meet after the first 10 patients are enrolled and have completed 2 cycles consolidation durvalumab, or after 4 patients of the first 10 in the safety run-in cohort have experienced DLT (whichever comes first), to review data for stopping rules as above. Additional DSMB meetings may be convened upon request of the sponsor-investigator, DSMB, or other applicable oversight body.

After the safety lead-in period, the next regular meeting will occur within 6 months of the 11th subject beginning study drug administration. The DSMB will continue to meet approximately every 6 months during the active study drug administration of the study. At the discretion of the DSMB, they may meet more frequently during the course of the study, as more data becomes available. The timing of the next scheduled meeting will be documented in the minutes from the prior meeting.

The DSMB will review the data regularly until at least 100 days after the last participant goes off study treatment. At this point, the DSMB will conduct reviews as needed until the study terminates.

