APPENDIX A: DOSING MODIFICATION AND TOXICITY MANAGEMENT  
GUIDELINES (TMGS) FOR DURVALUMAB MONOTHERAPY, DURVALUMAB IN  
COMBINATION WITH OTHER PRODUCTS, OR TREMELIMUMAB MONOTHERAPY –  
28OCT2021

General Considerations Regarding Immune-Mediated Reactions

These guidelines are provided as a recommendation to support investigators in the management of potential immune-mediated adverse events (imAEs).

Immune-mediated events can occur in nearly any organ or tissue, therefore, these guidelines may not include all the possible immune-mediated reactions. Investigators are advised to take into consideration the appropriate practice guidelines and other society guidelines (e.g., NCCN, ESMO) in the management of these events. Refer to the section of the table titled “Other Immune-Mediated Reactions” for general guidance on imAEs not noted in the “Specific Immune-Mediated Reactions” section.

Early identification and management of immune-mediated adverse events (imAEs) are essential to ensure safe use of the study drug. Monitor patients closely for symptoms and signs that may be clinical manifestations of underlying immune-mediated adverse events. Patients with suspected imAEs should be thoroughly evaluated to rule out any alternative etiologies (e.g., disease progression, concomitant medications, infections). In the absence of a clear alternative etiology, all such events should be managed as if they were immune-mediated. Institute medical management promptly, including specialty consultation as appropriate. In general, withhold study drug/study regimen for severe (Grade 3) imAEs. Permanently discontinue study drug/study regimen for life-threatening (Grade 4) imAEs, recurrent severe (Grade 3) imAEs that require systemic immunosuppressive treatment, or an inability to reduce corticosteroid dose to 10 mg or less of prednisone or equivalent per day within 12 weeks of initiating corticosteroids.

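### Read literally, the DLT list in Section 5.4.1 omits a fatal immune-mediated event (other than colitis or neurotoxicity) with no qualifying lower-grade event on record

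*Combined protocol and SAP*

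**What the plan says.** Section 5.4.1 grades events by CTCAE v5 and lists what counts as a DLT. Some lines are open at the top: any grade of febrile neutropenia, any grade of immune-mediated neurotoxicity, Grade ≥ 3 colitis, and Grade ≥ 3 events that are not immune-mediated. Others name a single grade:

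- "Any Grade 4 immune-mediated adverse event (imAE"
- "Grade 3 non-infectious pneumonitis irrespective of duration"
- "Grade 2 pneumonitis that does not resolve to" Grade 1 or lower within 3 days of maximal supportive care
- a Grade 3 immune-mediated event, colitis and pneumonitis apart, "that does not downgrade to Grade 2 within 3 days after onset of the event" or does not settle further within 14 days
- a Grade 3 transaminase rise with raised bilirubin

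No line mentions death or Grade 5.

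Section 5.4 halts enrollment at 3 DLTs in the first 5 patients or 4 in the first 10. Run-in patients who do not complete the DLT period "for reasons other than DLT will be replaced with another subject". Section 12.7 bases the thresholds on a sequential probability ratio test of a 10% against a 30% DLT rate, with type I error 0.05 and power 0.8.

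Two other places bear on the reading. Section 5.6 names "pancreatitis, myocarditis, myositis/polymyositis and rare/less frequent imAE" among immune-mediated events, and also classes infusion-related and anaphylactic reactions as immune-mediated. Appendix A describes Grade 4 as life-threatening: "Permanently discontinue study drug/study regimen for life-threatening (Grade 4) imAEs".

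**The concern.** The list uses at-or-above signs and any-grade wording where it wants an open-ended category, so a bare grade invites the reader to take it as that grade only. On that reading the general immune-mediated line stops at Grade 4, and the line for non-immune events cannot pick up the remainder because the event is immune-mediated. A patient who dies abruptly of an immune-mediated event, with nothing qualifying recorded beforehand, would have no DLT. That patient would also have left the DLT period for a reason other than a DLT, so Section 5.4 would call for a replacement.

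The run-in halting rule counts only DLTs. Its thresholds are 3 and 4 events, so one patient can decide whether enrollment stops for re-evaluation. A rule of this kind should not depend on readers supplying a missing sign for the worst possible outcome.

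**Working it through.** **Thresholds reproduced.** Inputs from Section 12.7: p0 = 0.10, p1 = 0.30, type I error 0.05, power 0.8. The upper boundary of Wald's sequential probability ratio test is the smallest k with

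k·ln(p1/p0) + (n − k)·ln((1 − p1)/(1 − p0)) ≥ ln(0.8/0.05) = ln 16 = 2.773.

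Here ln(0.30/0.10) = 1.0986 and ln(0.70/0.90) = −0.2513, so k ≥ (2.773 + 0.2513n)/1.3499.

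- n = 5: k ≥ 2.98, so 3.
- n = 10: k ≥ 3.92, so 4.

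Both agree with the plan. The thresholds do not depend on the wording at issue.

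**Each type of event at Grade 5, read literally.** Grade 5 is the fatal grade of the CTCAE scale that the protocol adopts.

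| Fatal event, no qualifying lower grade recorded | Line that could apply | DLT? |
|---|---|---|
| Immune-mediated neurotoxicity | any grade | yes |
| Colitis | Grade ≥ 3 | yes |
| Febrile neutropenia | any grade | yes |
| Event that is not immune-mediated | Grade ≥ 3 | yes |
| Immune-mediated pneumonitis | Grade 3; unresolved Grade 2; Grade 4 immune-mediated | no |
| Other immune-mediated event (myocarditis, hepatitis, anaphylaxis) | Grade 4; non-improving Grade 3; Grade 3 transaminases with bilirubin | no |

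At Grade 4 every class is covered. The gap is confined to the last two rows. It closes for any patient who first had a recorded Grade 4 immune-mediated event, Grade 3 pneumonitis, unresolved Grade 2 pneumonitis, a Grade 3 immune-mediated event that did not improve, or Grade 3 transaminases with raised bilirubin.

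**One sign is enough.** With the general line at Grade ≥ 4, both of the last two rows become DLTs. Fatal pneumonitis that is not immune-mediated is already a Grade ≥ 3 non-immune event.

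**Illustrative size.** The documents give no rate for such deaths, so the values below are pure assumptions. Let 30% be the assumed combined rate of DLTs plus uncounted fatal immune events, and let g be the share of patients with such a death who are replaced. The DLT rate among patients who count is q = (0.30 − g)/(1 − g). The halting probability is

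H(q) = P(≥ 3 of 5) + P(< 3 of 5 and ≥ 4 of 10), by exact binomial.

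- All counted: H(0.30) = 0.1631 + 0.2095 = 0.3726.
- g = 0.001: q = 0.299/0.999 = 0.2993, H = 0.3708, a fall of 0.2 points.
- g = 0.005: q = 0.295/0.995 = 0.2965, H = 0.3633, a fall of 0.9 points.

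The chance of at least one such death in 10 patients is 1 − (1 − g)^10, which is 1.0% and 4.9% respectively.

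**The case against.** The best case for leaving the text alone has three parts.

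First, the natural reading counts the death. Appendix A equates Grade 4 with life-threatening, and Section 11.1.2 defines life-threatening as being at risk of death at the time of the event, which a fatal event plainly satisfies. The list is loosely worded elsewhere: its requirement that a Grade 3 event improve to Grade 2 must mean Grade 2 or lower. This stands as evidence of intent. It does not remove the gap, because Section 11.1.2 lists death separately from life-threatening events and the adopted scale has its own fatal grade.

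Second, the safeguards do not depend on the DLT label. Enrollment pauses at 5 and at 10 patients whatever the count. A death not clearly due to progression is an SAE (Section 11.1.6), reportable within 1 business day (Section 11.2.2.1). At both pauses the DSMB sees adverse event summaries and "Data related to stopping/decision rules described in study design". Meeting the rule only halts accrual for re-evaluation. All of this stands and lowers the severity, but none of it adds the death to the DLT count.

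Third, the size is speculative. That also stands. A reader might take 30% as the plan's alternative DLT rate and infer that the wording costs the rule power at its design point. It does not: if DLTs as literally listed occur in 30% of the patients who count, the halting probability is still 37.3%. The falls arise only when 30% is taken to include the uncounted deaths. Nor do the documents support assuming rates high enough to make the loss look large.

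**Conclusion.** The point holds as a drafting gap of low severity. Followed exactly as written, Sections 5.4 and 5.4.1 would replace, and not count, a patient with a Grade 5 immune-mediated event other than colitis or neurotoxicity when no qualifying lower-grade event is on record. No other section makes such a death a DLT.

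Stronger inferences are not supported:

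- **Treatment-related deaths in general go uncounted.** They do not. Fatal colitis, fatal neurotoxicity, fatal non-immune events and deaths after a qualifying recorded event all count already.
- **The plan means to exclude fatal events, or leaves patients unprotected.** The intent was almost certainly to count them, and the SAE and DSMB provisions would likely bring such a death to attention.
- **The thresholds are wrong because of this wording.** They reproduce, and they stay as they are.

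On the stated assumptions the effect on the halting probability is 0.2 to 0.9 points. The text reading is firm; the numerical size is illustration only.

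**What to change.** In Section 5.4.1, change the general immune-mediated line from Grade 4 to Grade ≥ 4. That alone closes the gap. The death is then a DLT, and the existing replacement sentence in Section 5.4 no longer reaches the patient, so no separate sentence about deaths is needed.

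Optionally, and for consistency only, write the non-infectious pneumonitis line as Grade ≥ 3.

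The cost is one sign, or two with the optional edit, in one list. The thresholds of 3 of 5 and 4 of 10, the replacement rule, the sample size and the study procedures do not change.
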